#### 4.1.2.2 SECONDARY SAFETY ENDPOINTS

- Safety, including incidence of post-transplant infections, malignancies, morbidity, and other AEs (e.g., increased body weight and hypertension) associated with conventional immunosuppression.
- Renal function as measured by serum creatinine, GFR and other relevant laboratory parameters.
- Lipid profiles (triglycerides, total cholesterol, LDL cholesterol, HDL cholesterol) over time.

At  $75 \pm 5$  days following each transplant, at  $365 \pm 14$  days following the first and final islet transplant, and at two years following the final islet transplant:

- The incidence and severity of AEs related to the islet transplant procedure including: bleeding (> 2 g/dL decrease in hemoglobin concentration); segmental portal vein thrombosis; biliary puncture; wound complication (infection or subsequent hernia); and increased transaminase levels (> 5 times upper limit of normal [ULN])
- The incidence and severity of AEs related to the immunosuppression including: allergy; reduction in GFR; addition or intensification of anti-hypertensive therapy;

- gastrointestinal toxicity; neutropenia, anemia, or thrombocytopenia; viral, bacterial, or fungal infections; and benign or malignant neoplasms
- The incidence of a change in the immunosuppression drug regimen
  - The incidence of immune sensitization defined by presence of anti-HLA antibodies absent prior to transplantation
  - The incidence of discontinuation of immunosuppression

At  $365 \pm 14$  days following the first islet transplant:

- The incidence of worsening retinopathy as assessed by change in retinal photography from pre-transplant. If pupil dilation is not possible, then a manual ophthalmologic evaluation can be substituted.

## 5. STUDY TREATMENT REGIMEN

Please refer to section 1.5 and to applicable Package Inserts and product labeling for known and potential risks to human subjects associated with the study medication(s).

	Days Relative to Transplant																	
	0	1	2	3	4	5	6	7	8	9	10	14	28	42	56	84	85 - 730	
Islet Transplant	X																	
Belatacept	X				X							X	X		X	X	↔ q 4 weeks	
Basilixumab	X				X													
MMF		↔																

*Figure 2: Study Treatment Regimen*

### 5.1 Investigational Agents

The investigational agents for this study:

- Allogeneic islets: The allogeneic islets are considered the primary investigational agent being regulated by the FDA under DAIT, NIAID’s BB-IND 9336.
- NUJOLIX® (belatacept) : Belatacept is considered the secondary investigational agent in this study.

#### 5.1.1 Allogeneic Islets

##### 5.1.1.1 FORMULATION, DOSAGE, AND ADMINISTRATION

The final product is a 200 mL sterile suspension of ≥70% viable, ≥30% pure, allogeneic human purified islets in CMRL 1066 Transplant Media for administration by intraportal infusion. The final product is supplied in up to three 200 mL Ricordi® bags, containing a dose of ≥5,000 IEQ/kg recipient body weight (BW) for the first transplant, and ≥4,000 IE/kg recipient BW for subsequent transplants.

**Final Product Formulation:** Table 1: Composition of final drug product [Product Code PHPI-A-01]

Component	Quantity per Batch
Purified Human Pancreatic Islets	$\geq 4.0 \times 10^3$ IEQ /kg recipient BW (total IEQ/infusion)
CMRL 1066 Transplant Media, with HEPES and without sodium bicarbonate	q.s. to 200 mL per bag
Human Serum Albumin (HSA), USP	2.5%

**Administration:**

The islet mixture is delivered slowly via gravity drainage from a bag attached to the catheter in the portal vein or portal vein tributary. Access to the portal vein is achieved by percutaneous transhepatic access under fluoroscopic, ultrasonographic, or real-time CT guidance. Alternatively, access to a mesenteric or omental venous tributary of the portal vein can be obtained by mini-laparotomy under general anesthesia (transplant site preference or in the rare circumstance that percutaneous access cannot be achieved).

At a minimum, portal pressure will be monitored before and after infusion of each bag of the islet product, as well as after the final wash. Portal pressure measurements will be documented in the medical record.

Additional guidelines for islet administration and portal pressure measurements are located in the Manual of Procedures; however, each participating site should follow its site-specific standards to ensure compliance with institutional guidelines and subject safety.

**5.1.2 NUJOLIX® (belatacept)****5.1.2.1 FORMULATION, PACKAGING, AND LABELING**

NUJOLIX® (belatacept) for injection, 100 mg/vial or 250 mg/vial is a sterile non-pyrogenic lyophilized powder. Each 100-mg vial contains 110 mg of belatacept, 220 mg of sucrose, 15.18 mg of sodium phosphate monobasic monohydrate, 2.55 mg sodium chloride, and 1N sodium hydroxide/1N hydrochloric acid solution sufficient to adjust the pH to 7.5; each 250-mg vial contains 275 mg of belatacept, 550 mg of sucrose, 38.0 mg of sodium phosphate monobasic monohydrate, 6.4 mg of sodium chloride, and 1 N sodium hydroxide/ 1 N hydrochloric acid solution sufficient to adjust the pH to 7.5. The product includes a 10% overfill to account for vial, syringe and needle holdup. The lyophilized powder is provided in Type 1 glass vials, stoppered with gray butyl stoppers and sealed with aluminum seals.

NUJOLIX® (belatacept) for injection, 100 mg/vial or 250 mg/vial will be provided as open-label supplies packaged in boxes. Each box of 100 mg/vial will contain 16 vials; each box of 250 mg/vial will contain 8 vials. Each box will be labeled with a 1-panel, open label printed in black. The protocol number (CIT04), product identity and strength, container number range, batch number, the number of vials, directions for use, route of administration and storage conditions will be indicated.

### 5.1.2.2 PREPARATION, ADMINISTRATION, AND DOSAGE

All constitution and dilution of belatacept 100mg or 250mg vials must be performed using silicone free disposable (Norm-Ject®) syringes manufactured by Henke Sass Wolf in Germany, and administered through a sterile, non-pyrogenic, low protein binding in-line filter.

NOTE: It is recommended that a separate needle and syringe be used to withdraw the drug product solution from each vial.

Belatacept 100 mg vials (are sealed under vacuum. If any vials are found without this vacuum, they should be segregated and destroyed. Belatacept 250 mg vials are not sealed under vacuum.

Each 100mg vial of belatacept should be constituted with 4.2 mL of Sterile Water for injection to yield an approximate concentration of 25 mg/mL of belatacept; each 250 mg vial of belatacept should be constituted with 10.5 mL of Sterile Water for injection to yield an approximate concentration of 25 mg/mL of belatacept. To avoid foam formation, the stream of sterile water for injection should be directed to the sides of vial and should be constituted with gentle swirling until a clear solution is obtained. A sufficient excess of belatacept is incorporated into each vial to account for withdrawal losses so that 100 mg of belatacept can be withdrawn from the vial as 4 mL of a 25-mg/mL solution, or 250 mg of belatacept can be withdrawn from the vial as 10 mL of a 25-mg/mL solution. After initial constitution of the product to a concentration of 25 mg/mL, the solution may be diluted further with 5% Dextrose for Injection or 0.9% Normal Saline Solution to final belatacept concentrations as low as 1 mg/mL.

The final belatacept solution should be visually inspected for particulate matter prior to administration.

The continuous infusion solution must be filtered upon administration using an in-line, sterile, non-pyrogenic, low protein-binding filter with a pore size of 1.2 µm (to be provided by BMS). This infusion should be administered over a period of approximately 30 minutes. Any unused portion of the infusion solution should not be stored for reuse.

No incompatibilities have been observed with glass bottles or polyvinyl chloride bags and administration sets.

No data are available on the compatibility of belatacept with other IV substances. Other drug substances should not be added or infused simultaneously through the same IV line. Assure adequate, appropriate flushing between each drug substance if multiple drugs are administered through the same line sequentially.

Recommended safety measures for preparation and handling include protective clothing, gloves, and safety cabinets.

Subjects will receive NULOJIX® (belatacept) 10mg/kg through a peripheral vein on Day 0 and post-operative days 4, 14, 28, 56, 84. After Day 84 subjects will receive belatacept at a maintenance dose of 5 mg/kg every 4 weeks for the duration of study follow-up (2 years after the final islet transplant). Infusion of the Day 0 dose should be started after the islet product is deemed suitable for transplant and completed prior to beginning the transplant. Infusion doses will be based upon the subject's actual body weight at study Day 0 and will not be modified

during the course of the study unless there is a change in body weight  $\pm 10\%$  of the Day 0 weight. For second or third islet transplants performed after day 85, subjects will remain on the current maintenance dose and schedule of belatacept (5 mg/kg monthly), without modification. In addition to the maintenance doses, subjects will receive a single supplementary dose of belatacept 10 mg/kg. If the second or third transplant is performed within 14 days after the last dose of belatacept, the supplementary dose will be administered approximately 14 days (within the  $\pm 4$  day visit window) after the last dose of belatacept. If the transplant is performed more than 14 days of the last dose of belatacept, the supplementary dose will be administered within 24 hours of the transplant. This supplementary dose was chosen so as to approximate serum trough concentrations that are attained in the first 6-8 weeks after the initial transplant.

NOTE: If the maintenance dose is scheduled to be given within four days of a supplemental dose, the maintenance dose should not be given. Subjects will resume maintenance dosing at their next scheduled visit.

Currently, there is no existing long-term extension study for subjects who complete the study (CIT04) and receive belatacept (LEA29Y). Therefore, subjects may not be able to continue taking belatacept upon completion of the study. It is possible that a long-term extension study with belatacept may be conducted in the future and subjects may be eligible for this study if all inclusion and exclusion criterion are met. This will be detailed in a separate protocol, and a separate informed consent will be required. In the event a subject is not eligible, or the study is not implemented, clinical care beyond the completion of this study (CIT04) should be discussed between the subject and his/her islet transplant physician.

#### 5.1.2.3 HANDLING, DISPENSING, AND DESTRUCTION OF BELATACEPT

Care should be taken when handling the injectable drug products found in the protocol. Proper aseptic techniques should be used when preparing and administering sterile products such as belatacept.

The belatacept for injection 100 mg or 250 mg vial should be stored under refrigeration (2-8°C), and should be protected from long term exposure to light. Intact vials are stable for at least 1 year under these conditions.

Constituted solutions of belatacept at a concentration of 25 mg/mL are stable for 24 hours in the vials if stored at room temperature (15-25°C) and ambient lighting conditions, or under refrigeration. When further diluted with 5% Dextrose for Injection or 0.9% Normal Saline Solution to a belatacept concentration as low as 1 mg/mL, solutions may be stored in plastic, non-siliconized IV bags for up to 24 hours at room temperature and ambient lighting conditions or under refrigeration.

Belatacept should be stored in a secure area according to local regulations. It is the responsibility of the Investigator to ensure that belatacept is only dispensed to study subjects. Belatacept must be dispensed only from official study sites by authorized personnel according to local regulations. The Investigator should ensure that belatacept is stored in accordance with the environmental conditions (temperature, light and humidity) as determined by the Sponsor and defined in the Investigator Brochure or SmPC/reference label.

If an investigational product is destroyed at the site, it is the investigator's responsibility to ensure that arrangements have been made for the disposal, procedures for proper disposal have been established according to applicable regulations and guidelines and institutional procedures, and appropriate records of the disposal have been documented. The unused investigational products can only be destroyed after being inspected and reconciled by the responsible study monitor.

### **5.1.3 Drug Accountability**

Under Title 21 of the Code of Federal Regulations (21CFR §312.62)), the investigator is required to maintain adequate records of the disposition of the investigational agent, including the date and quantity of the drug received, to whom the drug was dispensed (subject-by-subject accounting), and a detailed accounting of any drug accidentally or deliberately destroyed.

Records for receipt, storage, use, and disposition must comply with applicable regulations and guidelines and will be maintained by the study site. Records should include:

- The amount of study drug received and placed in the storage area;
- The amount of drug currently in the storage area;
- Label identification number or batch number and use data or expiry date;
- Amount dispensed to and returned by each subject, including unique subject identifiers
- Non-study disposition (e.g., lost, wasted, broken)
- Amount returned to the sponsor
- Amount destroyed at study site, if applicable
- Retained samples sent to a third party for bioavailability/bioequivalence, if applicable.
- Dates and initials of person responsible for each investigational product inventory entry/movement; and
- Amount transferred to another area for dispensing or storage.

In addition, a drug-dispensing log will be kept current for each subject. This log will contain the identification of each subject and the date and quantity of drug dispensed.

All records regarding the disposition of the investigational product will be available for inspection by the clinical trial monitor.

## **5.2 Immunosuppression Medications**

The immunosuppressive agents used for the initial and subsequent islet transplants will be identical.

### **5.2.1 Mycophenolate Mofetil (Cellcept®)**

Subjects will receive mycophenolate mofetil starting immediately pre-transplant on Day 0 at a dose of 1g PO BID.

If a subject experiences severe neutropenia (absolute neutrophil count  $<1 \times 10^9/L$ ), gastrointestinal toxicity, or other side effects requiring a dose reduction, then the MMF dose may be adjusted at the investigator's discretion (see section 5.7.1 for guidelines). If the dose is less than 500 mg BID, then a mycophenolic acid (MPA) blood trough level will be drawn. If the MPA level is below therapeutic range (reference range  $< 1 \mu\text{g/ml}$  or lower end of reference range at institution) in the absence of infectious complications, then tacrolimus will be added to the immunosuppressive regimen.

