### **2.2 Secondary Objectives**

The secondary objective is to assess islet graft function in the absence of calcineurin inhibitor drugs, with determination of success being the proportion of patients attaining and maintaining insulin independence after receiving a maximum of 3 islet transplants.

Additional objectives are to obtain samples for the islet and immune function mechanistic studies which are described in Section 9.

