## 4. STUDY DESIGN

This trial is a prospective, two-center, open-label, pilot study of islet transplantation assessing the safety and efficacy of a steroid-free, calcineurin inhibitor-free belatacept based immunosuppressive medication in subjects with long-standing T1D that is refractory to intensive insulin therapy. The two centers participating in this phase 2 study will also undertake a separate, phase 3 study in islet transplantation, using a standard manufacturing and immunosuppressive regimen. The phase 3 trial, Protocol CIT07, will have inclusion/exclusion criteria and endpoint measures that are identical to those in this phase 2 trial. In order to avoid bias in selection of subjects, eligible subjects will be randomized, prior to transplantation, to participate either in this phase 2 or the multi-center phase 3 study.

Subjects who meet the general inclusion/exclusion criteria will be approached regarding their participation. Subjects who sign informed consent will be enrolled and assigned a unique subject identification number. Subjects will then be formally evaluated for eligibility through the performance of screening visit procedures. More than one visit may be necessary to complete all of the screening procedures. The two participating centers will accrue subjects over a 24 month period and will treat a total of 10 study subjects. No one center will treat more than 12 subjects.

Figure 1: Study Design Schema.

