### **5.2.3 Tacrolimus (Prograf®)**

Tacrolimus may be used only as a supplement to MMF in those cases where the trough level is below the therapeutic range as outlined in section 5.2.1. Tacrolimus will be administered orally twice a day to maintain trough levels of 3-5 ng/mL. Generic equivalents of Prograf® will not be permitted.

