## 5.7 Modification or Discontinuation of Study Treatment

### 5.7.1 Modification of Consensus Immunosuppression

#### 5.7.1.1 INTOLERANCE OF PROTOCOL MEDICATIONS

In the event that protocol-regulated concomitant medications are not tolerated, the subject will continue taking the immunosuppressive therapy in order to protect the islet graft. In the event that the immunosuppression regimen is not tolerated, the Site principal investigator (PI) may elect to prescribe an alternative immunosuppression regimen. The intent would be for the alternative regimen to be temporary in nature where possible. Any non-protocol directed study treatment modification that the site PI determines is necessary should be reported as a protocol deviation.

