## **10. STATISTICAL CONSIDERATIONS AND ANALYTICAL PLAN**

### **10.1 Analysis Samples**

The details of the analyses will be provided in the statistical analysis plan (SAP). All primary and secondary analyses will be done using the intention to treat principal. Every subject who receives belatacept or islets will be accounted for in the analysis.

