### **10.2 Study Endpoint Assessment**

#### **10.2.1 Primary Endpoint**

The primary objective of the analysis is to estimate the rate of insulin independence at 75 days after the first islet transplant. The primary endpoint is insulin independence (yes/no) at day 75 after islet transplant as defined in section 4.1.1. The primary analysis will compute an exact binomial estimate and a 95% confidence interval for the true rate. If the results of this trial show at least 10% insulin independence in the context of evaluation all of the secondary endpoints, the investigators will consider this grounds for further investigation.

The primary analysis will consist of the intent-to-treat population. An exception will be if a death occurs or if the subject withdraws consent to be followed, in these cases the endpoint will be classified as failure to achieve insulin independence. Should the endpoint not be evaluated for a particular individual for other reasons, a failure will be imputed unless an evaluation is done at a time longer than 75 days after transplant and before an additional islet transplant, in which case that later value will be imputed. All imputations will be reported with the primary analysis.

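### The secondary objective is graft function without calcineurin inhibitors, but the protocol directs tacrolimus for some subjects and counts them like any other, so the reported rate can exceed the calcineurin-inhibitor-free rate

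*Protocol*

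**What the plan says.** **Objective and measure.** Section 2.2 states: "The secondary objective is to assess islet graft function in the absence of calcineurin inhibitor drugs". The same sentence gives the measure as "determination of success being the proportion of patients attaining and maintaining insulin independence after receiving a maximum of 3 islet transplants", with no condition on CNI use. Section 4 calls the treatment under study a "steroid-free, calcineurin inhibitor-free belatacept based immunosuppressive medication".

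**Tacrolimus provision.** Section 5.2.1 has three conditions: MMF dose below 500 mg BID, mycophenolic acid below the therapeutic range, and no infectious complications. When they are met, "then tacrolimus will be added to the immunosuppressive regimen". Section 5.2.3 adds: "Tacrolimus will be administered orally twice a day to maintain trough levels of 3-5 ng/mL". No end date is given. Section 1.4.1.1 itself classes tacrolimus as a calcineurin inhibitor.

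**Analysis rules.** Section 10.1 states: "All primary and secondary analyses will be done using the intention to treat principal". The Study Definitions base insulin independence on insulin use, HbA1c, glucose and C-peptide. Immunosuppression plays no part. For the primary endpoint, Section 10.2.1 assigns failure for death, for withdrawal of consent, and for an endpoint not evaluated (unless a later evaluation precedes another transplant). Section 10.2.2 applies similar methods to secondary endpoints, without imputation. A change of immunosuppressive regimen is counted only as a safety endpoint, in Section 4.1.2.2.

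**The concern.** A subject can follow the protocol exactly and still reach the efficacy assessment on the drug class whose absence defines the secondary objective. Section 1.4.2 gives the scientific reason for caring: the hypothesis is that avoiding tacrolimus and sirolimus favours engraftment and function. A reader of the final report will take a single insulin-independence rate from a trial described as CNI-free to be a rate achieved without CNIs. If some of the successes were on tacrolimus, that reading is wrong, and nothing in the planned efficacy output would show it. In a trial of 10, even one such subject is visible in the estimate.

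**Working it through.** **1. The plan's own intervals.** Table 5 (Section 10.4) gives exact 95% intervals for n = 10. The two-sided Clopper-Pearson limits for x successes are

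- lower = 2.5% quantile of Beta(x, n − x + 1), set to 0 when x = 0;
- upper = 97.5% quantile of Beta(x + 1, n − x), set to 1 when x = n.

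All 11 rows of Table 5 reproduce to four decimals, for example 5/10: 0.1871 to 0.8129.

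**2. How a tacrolimus-treated subject is scored.**

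- Received belatacept or islets: in the analysis set (Section 10.1).
- Tacrolimus added under Section 5.2.1: protocol-directed treatment, and not among the reasons for premature discontinuation in Section 5.7.2.
- Alive, consenting and evaluated: none of the failure rules in Section 10.2.1 applies.
- Insulin, HbA1c, glucose and C-peptide criteria met: insulin independent under the Study Definitions.

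The subject is a success. No sentence says so directly. It follows from the stated rules taken together.

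**3. Size of the gap.** Let s be the number insulin independent among 10, and k the number of those who received a CNI before the assessment.

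- ITT rate = s/10.
- CNI-free success rate, all subjects in the denominator = (s − k)/10.
- Difference = k/10, that is 10 percentage points per subject.

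The values of s and k below are illustrations, since the protocol gives neither.

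| s | k | ITT rate | CNI-free rate | Exact 95% CI for CNI-free rate |
|---|---|---|---|---|
| 5 | 0 | 50% | 50% | 0.1871 to 0.8129 |
| 5 | 1 | 50% | 40% | 0.1216 to 0.7376 |
| 5 | 2 | 50% | 30% | 0.0667 to 0.6525 |
| 5 | 3 | 50% | 20% | 0.0252 to 0.5561 |
| 3 | 1 | 30% | 20% | 0.0252 to 0.5561 |
| 3 | 2 | 30% | 10% | 0.0025 to 0.4450 |
| 3 | 3 | 30% | 0% | 0 to 0.3085 |

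**4. Choice of denominator.** Dropping the tacrolimus subject from both counts would turn 5/10 with k = 1 into 4/9 = 44.4% (0.1370 to 0.7880). That excludes a subject because of something that happened after transplant, so the full denominator is preferable.

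**The case against.** **ITT is the right analysis.** Tacrolimus is a planned contingency, and ITT estimates the success rate of the strategy as delivered. This stands, and the ITT rate should remain. It does not answer the question Section 2.2 asks.

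**Section 2.2 attaches no CNI condition to its success measure.** This also stands. The CNI phrase belongs to the objective, and the measure is insulin independence alone. That is the mismatch: objective and measure in the same sentence do not correspond once Section 5.2.1 operates. A CNI-free rate is therefore an additional measure, not one the protocol already defines.

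**Such detail belongs in the SAP.** In part. The protocol, however, itself fixes the objective, the measure, the analysis principle and the failure events, and these do not fit together. The sensitivity analysis that Section 10.2.2 leaves to the SAP concerns missing values, and these subjects are not missing.

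**The direction is uncertain.** Section 1.5.5.2 describes tacrolimus as toxic to beta cells, so a success on it may have come despite the drug. This stands against a hypothetical outcome with no tacrolimus given. The ITT rate is certain not to fall below the rate of being insulin independent with no prior CNI use, but that is the only comparison with a known direction.

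**Stronger readings that the documents do not support.**

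- A reader might infer that one success on tacrolimus would carry the trial past its threshold for further work ("If the results of this trial show at least 10% insulin independence"). That threshold belongs to the Day 75 primary endpoint, whose objective in Section 2.1 does not mention CNI absence. The same sentence requires it to be read with all secondary endpoints, which include regimen change.
- A reader might treat Section 5.7.2 as the route that keeps these subjects in the analysis. It concerns stopping study treatment, not adding tacrolimus.
- A reader might estimate tacrolimus use from the renal trial in Section 1.2.2, where leukopenia was reported in 16.9% to 18.9% of belatacept subjects. Those are adverse-event rates over a mean exposure of 300 to 308 days. They are not rates of meeting the three conditions of Section 5.2.1, still less of being insulin independent as well.
- Section 5.7.1.1, under which the site investigator "may elect to prescribe an alternative immunosuppression regimen", adds little. Those changes are meant to be temporary where possible, and non-protocol modifications are reported as deviations.

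**Conclusion.** The point holds as a mismatch between the CNI-free objective and the rules that will produce its estimate. The ITT rate can exceed the rate of CNI-free insulin independence by 10 percentage points for each subject who is insulin independent after receiving a CNI. This assumes 10 analysed subjects and that such subjects meet every insulin-independence criterion. How many there will be is unknown, because the protocol gives no tacrolimus rate. If there are none, the two rates coincide. The primary analysis and its 10% criterion are not called into question. One further limit is that the Section 2.2 measure does not appear in the endpoint list of Section 4.1.2, although Section 10.2.2 gives insulin independence at one year after the first transplant as an example of a secondary proportion. The time point for the comparison therefore has to be named.

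**What to change.** 1. Reconcile the CNI-free wording in Sections 2.2 and 4 with the tacrolimus provision in Sections 5.2.1 and 5.2.3, so that the objective and the regimen describe the same thing. No view is taken here on the clinical rule itself.
2. Leave the ITT analysis and the primary 10% criterion unchanged.
3. For the Section 2.2 objective, name the assessment time and report, beside the ITT rate:
   - the number of subjects given any CNI before that assessment;
   - the proportion insulin independent without prior CNI use, with CNI users counted as not CNI-free successes, all subjects in the denominator, and an exact 95% CI.

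The cost is a few lines of text and one extra row in a table. Concomitant medications are already recorded (Section 10.3.3) and regimen changes already tabulated (Section 4.1.2.2). The downside is that the CNI-free rate may be lower than the ITT rate. It should also be labelled as a composite of outcome and treatment received, not as an estimate of what would have happened had tacrolimus not been given.
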